## 1.7 Study duration

The total study duration is estimated to be approximately 15 months. The study duration for subject enrolled prospectively is expected to be approximately 12 months.

## 1.8 Key Inclusion Criteria

Subjects who meet all the following criteria may be given consideration for inclusion in this clinical investigation, provided no exclusion criterion is met.

- Subjects have provided the written informed consent, are willing to participate in clinical data collection and willing to comply with study procedure. (for subjects enrolled prospectively).
- Subjects must have been pathologically confirmed prostate cancer with clinical stage T1-T2, and have been treated with Space OAR Hydrogel, and have received or will receive radiotherapy.

## 1.9 Key Exclusion Criteria

There is no specific exclusion criteria unless the patients refuse to sign the informed consent.

## 2 INTRODUCTION

The Statistical Analysis Plan (SAP) is based on SpaceOAR Observation-China protocol version B and the electronic case report form (eCRF) version 5.0. It documents the planned analysis outlined in the protocol, and is consistent with the study objective. Specified analyses may be used for scientific presentations and/or manuscripts, and regulatory submissions. This is an observational study to evaluate the safety and effectiveness of radiotherapy for localized T1-T2 prostate cancer in China after injection of SpaceOAR Hydrogel. This study protocol is for the second part of SpaceOAR real world study.

SpaceOAR system has been firstly used in Hainan BOAO as a licensed medical device, while there is no evidence about the radiotherapy after SpaceOAR hydrogel injection in China. As a result, an observational study is conducted to gather the relevant clinical data in Chinese

patients with localized PCa who receive radiotherapy after SpaceOAR hydrogel is injected. Due to limited patient pool in BOAO, the subjects will be enrolled prospectively and retrospectively to speed up the study recruitment.

### **3 ENDPOINT ANALYSIS**

#### **3.1 Primary Endpoints**

Reduction of dose volume of rectum receiving x Gy as specified below, which is measured from CT simulation scans acquired pre and post SpaceOAR hydrogel injection, (i.e. Vx Gy):

- For conventionally fractionated regimen: V70Gy
- For moderately hypofractionated regimen: V46Gy, V37Gy
- For ultrahypofractionated regimen: V29 Gy, V18. 1 Gy, V36 Gy

Dose to the anterior rectum is quantified by computing a rectal dose-volume histogram (DVH).

##### **3.1.1 Hypothesis**

There are no hypotheses for this second stage of the SpaceOAR Real World study. All the endpoints are descriptive in nature.

##### **3.1.2 Sample Size**

No formal sample size calculation is performed. The study plans to enroll up to 14 subjects.

To account for potential missing data in this retrospective and prospective study, a final sample size will be up to 20 subjects.

##### **3.1.3 Statistical Methods**

For continuous and ordinal variables, descriptive statistics will include number of observations, mean, standard deviation, minimum and maximum. Specific variables may also include additional statistics such as median, interquartile range (IQR) and confidence intervals. For binary or categorical variables, descriptive statistics will include percentage, numerator, denominator and number of missing observations if applicable. When the distribution of a variable does not support the use of parametric statistics, nonparametric approaches may be implemented. A parametric method of paired t-test or wilcoxon signed-rank non parametric test will be used for before and after clinical assessments.

#### **3.2 Secondary Endpoints**

- EPIC bowel and urinary assessment composite score at 2 weeks, 6 weeks, and 3 months post radiotherapy.
- EPIC sexual assessment composite score at 2 weeks, 6 weeks, and 3 months post radiotherapy.
- Quality of Life at 2 weeks, 6 weeks, and 3 months post radiotherapy (QOL).

- Whether there is SpaceOAR hydrogel between the posterior prostatic capsule and the anterior rectal wall at 6 weeks post radiotherapy.
- Whether the SpaceOAR hydrogel between the prostate and the anterior rectal wall is absorbed in 10 months post radiotherapy.
- Rectal adverse event (CTCAE).
- AEs/SAEs related to SpaceOAR hydrogel.

### **3.2.1 Hypothesis**

No formal tests of hypotheses are proposed for secondary endpoints.

### **3.2.2 Statistical Methods**

For continuous and ordinal variables, descriptive statistics will include number of observations, mean, standard deviation, minimum and maximum. Specific variables may also include additional statistics such as median, interquartile range (IQR) and confidence intervals. For binary or categorical variables, descriptive statistics will include percentage, numerator, denominator and number of missing observations if applicable. When the distribution of a variable does not support the use of parametric statistics, nonparametric approaches may be implemented. A parametric method of paired t-test or wilcoxon signed-rank non parametric test will be used for before and after clinical assessments.

## **4 GENERAL STATISTICAL METHODS**

### **4.1 Analysis Sets**

The effectiveness set, and safety set include all subjects who have radiotherapy after injection of SpaceOAR hydrogel.

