The target population in this study are patients diagnosed with localized prostate cancer who took part in SpaceOAR RWS in Hainan (U0720) and have been treated with SpaceOAR Hydrogel in hospital in Hainan Boao, are receive or will receive radiotherapy in this site.

7.3. *Inclusion Criteria*

Subjects who meet all the following criteria may be given consideration for inclusion in this clinical investigation, provided no exclusion criterion is met.

- Subjects have provided the written informed consent, are willing to participate in clinical data collection and willing to comply with study procedure. (for subjects enrolled prospectively)
- Subjects must have been pathologically confirmed prostate cancer with clinical stage T1-T2, and have been treated with Space OAR Hydrogel, and have received or will receive radiotherapy.

7.4. *Exclusion Criteria*

There are no specific exclusion criteria unless the patients refuse to sign the informed consent.

8. Subject Accountability

8.1. *Point of Enrollment*

During screening, patients who have received or will receive radiotherapy will be identified. These who have been injected with SpaceOAR hydrogel will be enrolled. For patients who have already received radiotherapy, the clinical data can be collected retrospectively, and informed consent will be performed (If follow up visits can be conducted prospectively). For patients who will receive radiotherapy, informed consent will be gained.

8.2. *Withdrawal*

All subjects enrolled in the clinical study (including those withdrawn from the clinical study) shall be accounted for and documented. If a subject withdraws from the clinical investigation, the reason(s) shall be reported. The applicable CRF(s), including the end of the study form, shall be completed at the time of subject withdrawal.

8.3. *Lost to Follow-Up*

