A subject will be considered lost to follow-up if he fails to complete 30 days follow-up visits and is unable to be contacted by the study site staff after at least three documented attempts, at which point an End of Study form should be completed. Before a participant is deemed lost to follow up, the investigator or designee will make every effort to regain contact with the participant (where possible, 3 telephone calls and, if necessary, a certified letter to the participant's last known mailing address or local equivalent methods). These contact attempts should be documented in the participant's medical record or study file. (only for patients enrolled prospectively).

8.4. *End-of-Study Definition*

A subject is considered to have completed the study if he has completed all phases of study including the last visit or last scheduled procedure shown in the data collection schedule.

A clinical trial is considered completed when participants are no longer being examined or the last participant's last study visit has occurred.

9. Study Methods

9.1. *Data Collection*

The data collection schedule is shown in Table 9-1.

Table 9-1: Data Collection Schedule

Procedure/Assessment	Before RT	RT	After RT			
			2W (\pm 3days)	6W (\pm 7days)	3M (\pm 15days)	10M (\pm 30 days)
Informed consent	X					
PSA	X			X		X
CT	X*					
MRI	X*			X		X
Radiotherapy		X				
EPIC questionnaire	X		X	X	X	
EQ-5D-5L questionnaire	X		X	X	X	
Concomitant medication	X	X	X	X	X	X
Adverse event	X	X	X	X	X	X
Protocol Deviation	X	X	X	X	X	X
Device Deficiency[#]	X	X	X	X	X	X

NOTE:1. Data at baseline such as demography, medical history, Pca, etc. refer to SpaceOAR RWS (U0720).
 2.*CT&MRI for mapping, which used to make RT planning, 2 times.
 3.# DD of Space OAR hydrogel.

9.2. *Study Candidate Screening*

Patients diagnosed with localized prostate cancer who have been injected with SpaceOAR hydrogel in SpaceOAR RWS in Hainan (U0720) will be invited to participate in this study.

9.3. *Informed Consent*

For patients who receive radiotherapy after SpaceOAR injected, investigator will introduce study information to subject and get ICF. Once the ICF is signed, he is enrolled in study. If he fails to receive radiotherapy after ICF signed, the subjects are screening failure.

9.4. *study visits*

The subject of SpaceOAR RWS are going to participate in this study when he completed last visit. the process of SpaceOAR RWS is summarized below.

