All subjects were treated with SpaceOAR system, which were implanted between prostate and anterior rectum before participation in this study. It slowly absorbs via hydrolysis and is cleared from the implant site in approximately six months. Anticipated adverse events and Anticipated Adverse Device Effects of SpaceOAR system are specified as below:

- Pain associated with SpaceOAR hydrogel injection
- Pain or discomfort associated with SpaceOAR hydrogel
- Local inflammatory reactions
- Infection
- Urinary retention
- Mucosal damage, ulcers
- Bleeding
- Constipation
- Urgency (e.g., urinary and rectal)
- Allergic reaction
- Embolism
- Fistula
- Penetration
- Syncope

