17.1. Reportable Events by investigational site to Boston Scientific

It is the responsibility of the investigator to assess and report to BSC any event which occurs in any of following categories:

- All adverse events
- All serious adverse events
- All Adverse Events related to Study Device
- All Serious Adverse Events related to Study Device
- All Adverse Events related to RT
- All Serious Adverse Events related to RT
- Unanticipated Adverse Device Effects/Unanticipated Serious Adverse Device Effects
- All Device Deficiencies
- New findings/updates in relation to already reported events

When possible, the medical diagnosis should be reported as the Event Term instead of individual symptoms.

If it is unclear whether an event fits one of the above categories, or if the event cannot be isolated from the device or procedure, it should be submitted as an adverse event and/or device deficiency.

Any reportable event, experienced by the study subject after informed consent, whether prior to, during or after RT, must be recorded in the eCRF.

Underlying diseases and chronic conditions are not reported as AEs unless there is an increase in severity or frequency during the investigation. Death should not be recorded as an AE, but should only be reflected as an outcome of one (1) specific SAE (see Table 17-1 for AE definitions).

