#### 5.2.4 Analysis of Adverse and Serious Adverse Events

Frequency of site reported Serious adverse events and Non-serious adverse events associated with the study device will be summarized. The events will be summarized by MedDRA system organ class and MedDRA system preferred terms with event counts and proportions. A listing based on all site reported adverse events with seriousness, relationships and duration days will be created. Similarly, a listing for all anticipated/unanticipated adverse device events with seriousness and duration from onset date will be also produced.

For calculating events and rates, 'Events numbers' are total number of episodes for each type of event among all subjects. 'Rate of Subjects with Event' numbers are percent of subjects who experienced one or more episodes of the event. 'Events' numbers for "TOTAL" are the sum of the individual event category totals. 'Rate of Subjects with Event' numbers for "TOTAL" is the percent of subjects who experienced at least one adverse event.

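### The only safety set requires radiotherapy and SAP 5.2.4 names no set, so on the natural reading a hydrogel-related event in a consented man who goes without radiotherapy is left out of the hydrogel AE rate

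*SAP*

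**What the plan says.** - **Analysis sets.** SAP 4.1 and Protocol 10.2.1 share one sentence for both populations: "The effectiveness set, and safety set include all subjects who have radiotherapy after injection of SpaceOAR hydrogel". Neither document defines an enrolled set or an injected set.
- **Status without RT.** Protocol 9.3: "Once the ICF is signed, he is enrolled in study. If he fails to receive radiotherapy after ICF signed, the subjects are screening failure".
- **Exposure.** Protocol 16.1: "All subjects were treated with SpaceOAR system, which were implanted between prostate and anterior rectum before participation in this study".
- **Endpoint.** SAP 3.2 and Protocol 5.2.2 list "AEs/SAEs related to SpaceOAR hydrogel" as a secondary endpoint.
- **Recording and accountability.** Protocol 17.1: "Any reportable event, experienced by the study subject after informed consent, whether prior to, during or after RT, must be recorded in the eCRF". Protocol 8.2: "All subjects enrolled in the clinical study (including those withdrawn from the clinical study) shall be accounted for and documented".
- **AE tables.** SAP 5.2.4 summarises device-associated serious and non-serious events. It counts the "total number of episodes for each type of event among all subjects" and gives rates as a percentage of subjects, without naming a set for either. It also plans a listing: "A listing based on all site reported adverse events with seriousness, relationships and duration days will be created".
- **Disposition.** SAP 5.2.3 covers follow-up compliance and deaths. It does not mention consented subjects who go without RT.

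**The concern.** Every man has had the hydrogel before he enters this study, so for a hydrogel-related event he is already exposed on the day he consents. Whether he counts in the safety set depends on something that happens later, namely receiving RT. A hydrogel complication could itself be the reason RT is not given. In that case the consequence of the event removes the man, and his event, from the rate meant to describe it. A hydrogel event in a man who misses RT for an unrelated reason would be left out in the same way.

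At stake is the point estimate for one secondary safety endpoint, and whether a given event is counted at all. SAP 3.2.1 proposes no formal test for the secondary endpoints, and no success threshold is set, so no decision rule is affected.

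**Working it through.** The plan states no AE rate and no rate of missed RT, so there is no figure to reproduce. The check has two parts: reading the text, and a scale calculation on assumed counts.

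**1. Following one man through the text.** He is injected in Hainan and consents to this study, so under Protocol 9.3 he is enrolled. He has a hydrogel-related event before RT, which Protocol 17.1 requires to be recorded in the eCRF. He does not receive RT, and 9.3 now calls him a screening failure. He does not meet the description in SAP 4.1. In SAP 5.2.4 the phrase *all subjects* could mean all enrolled subjects or all in the safety set. Since only one safety set exists and he carries the screening-failure label, the natural reading leaves him out of the numerator and the denominator. SAP 7.3 bases denominators on visit completers, which does not settle the matter for AE tables. The all-AE listing has no stated RT condition, so his event would probably still appear there.

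**2. Who can be affected.** Only prospective subjects who consent and then receive no RT. A retrospective subject has already completed RT.

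**3. Scale.** N is the number enrolled: 20 at most, 14 at least (SAP 1.3). Assumption: one man goes without RT. The rate in all enrolled, injected men is x/N. The rate in the RT-treated set is (x minus his events)/(N − 1), counting subjects with an event. Intervals are exact (Clopper-Pearson) 95%. For x = 0 the upper limit is 1 − 0.025^(1/n); for example n = 19 gives 1 − 0.025^(1/19) = 17.6%. For x = 1 the lower limit is 1 − 0.975^(1/n), and the upper limit solves (1 − p)^n + np(1 − p)^(n−1) = 0.025.

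| Case | All enrolled, injected | RT-treated only | Change (points) |
|---|---|---|---|
| (a) He has the only event, N = 20 | 1/20 = 5.0% (0.1–24.9) | 0/19 = 0% (0–17.6) | −5.0 |
| (a) He has the only event, N = 14 | 1/14 = 7.1% (0.2–33.9) | 0/13 = 0% (0–24.7) | −7.1 |
| (b) He has none, one other man does, N = 20 | 1/20 = 5.0% (0.1–24.9) | 1/19 = 5.3% (0.1–26.0) | +0.3 |
| (b) He has none, one other man does, N = 14 | 1/14 = 7.1% (0.2–33.9) | 1/13 = 7.7% (0.2–36.0) | +0.5 |
| (c) Every consented man receives RT | x/N | x/N | 0 |

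As an extreme, suppose three men go without RT, all three have a hydrogel event, and no RT-treated man does. Then 3/20 = 15.0% (3.2–37.9) becomes 0/17 = 0% (0–19.5), and 3/14 = 21.4% (4.7–50.8) becomes 0/11 = 0% (0–28.5). Nothing in the documents suggests that this is likely.

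In (a) and (b) the paired intervals overlap widely. What changes is the point estimate and whether the event is counted.

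**The case against.** The RT condition looks deliberate. Eligibility requires RT received or planned, the objective is the safety and effectiveness of radiotherapy in injected men, and 9.3 makes a man without RT a screening failure. A set without screening failures follows from that rule. This stands for effectiveness and RT-related AEs. It does not extend to the hydrogel endpoint, where exposure came earlier.

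The injection stage has its own study, U0720, with a 30-day AE call (timed from discharge in Protocol 7.1, from injection in 9.4), and 9.4 has men join after their last U0720 visit. Early complications may therefore be captured there. This stands in part. 9.4 lists planning and RT before that call, so the sequence is not strict. The gel takes about six months to clear (Protocol 16.1), well beyond 30 days. Capture in another study also does not complete this study's rate.

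Three stronger readings are tempting, and the documents do not support them:

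- *The safety set contradicts Protocol 8.2 and 17.1.* It does not. Those sections impose accountability and recording duties, and a man can be documented and recorded yet lie outside an analysis set. The wording tension is inside 9.3, which enrols a man and then calls him a screening failure.
- *Hydrogel events would be lost or hidden.* They must be recorded, and with at most 20 men an event in the listing is visible to a reader. What is missing is a place in the summarised rate.
- *The hydrogel rate will be too low.* The direction depends on who goes without RT, as cases (a) to (c) show, and there may be no such man. The exclusion is itself an inference: the set sentence says which subjects are included and does not literally say that no others are.

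**Conclusion.** The point holds as a minor one. A stated rule, together with an unnamed set in SAP 5.2.4, makes the hydrogel AE/SAE rate conditional on an event after exposure that a hydrogel complication could prevent. With one man affected, the shift is 5.0 to 7.1 percentage points downward if he has the only event, 0.3 to 0.5 points upward if he has none and one other man does, and zero if every consented man receives RT. All of these sizes rest on assumed counts. The conclusion also rests on reading *all subjects* in SAP 5.2.4 through SAP 4.1, which is the most natural reading but not the only one.

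**What to change.** Amend the SAP before analysis. Protocol 10.3 lets changes to the endpoint analyses be described in the SAP, and SAP 5.3 gives the amendment route, so no protocol amendment is needed for the following:

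- **SAP 4.1:** add a set of all enrolled subjects injected with the hydrogel, whether or not RT is given, for hydrogel-related AEs/SAEs. Keep the RT-treated set for effectiveness and RT-related AEs.
- **SAP 5.2.4:** name the set for each AE table, say what *all subjects* means, and show the hydrogel AE rate in the RT-treated set alongside.
- **SAP 5.2.3:** report consented subjects without RT, with reasons.
- **Limitations:** state that men who gave up RT before consenting are not captured here, and that earlier events may sit in U0720.

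At the next protocol amendment, reconcile the enrolment and screening-failure wording in 9.3. The analytic change does not depend on it.

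The cost is a few sentences and one table column; the events are already required in the eCRF. The drawback is unequal follow-up. Every post-treatment visit is timed from RT, so a man without RT has only the pre-RT assessment scheduled. Adding him can dilute the rate slightly (1/19 = 5.3% becomes 1/20 = 5.0% if he is event-free), which is why both rates should be shown.

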### **4.2 Control of Systematic Error/Bias**

All patients who receive RT at the BOAO site after injection of SpaceOAR will be invited to enroll at a given time, to minimize selection bias. The primary endpoint is an objective measure, which is computed via DVH to reduce assessment bias.

### **4.3 Method of handling missing, incorrect data (including subjects withdrawal and lost to follow-up) and unreasonable data**

Missing data will not be imputed for primary analysis. Incorrect and unreasonable data will be clarified before database lock. Imputation with mean or median may be performed where applicable for the primary endpoint as a sensitivity analysis. Visit-wise mean and LOCF imputation methods will be used for missing values.

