10.2.2. Control of Systematic Error/Bias

All patients who receive RT at the BOAO site after injection of SpaceOAR will be invited to enroll at a given time, to minimize selection bias. The primary endpoint is an objective measure, which is computed via DVH to reduce assessment bias.

10.2.3. The method of handling missing, incorrect data (including subjects' withdrawal and lost to follow-up) and unreasonable data

Missing data will not be imputed for primary analysis. Incorrect and unreasonable data will be clarified before database lock. Imputation with mean or median may be performed where applicable for the primary endpoint as a sensitivity analysis.

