#### 5.2.2 Post-procedure Analyses

Post-procedure information will be collected at 2 weeks, 6 weeks, 3 months and 10 months. And they will be summarized using descriptive statistics for continuous and frequency tables or proportions for discrete variables. No formal statistical testing will be performed.

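### SAP 4.3 requires visit-wise mean and LOCF imputation without naming an endpoint, analysis or order; applied to EPIC and EQ-5D-5L, mean fill understates standard errors and LOCF can shrink acute change

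*SAP*

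**What the plan says.** SAP 4.3 contains three statements on imputation, in this order.

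1. A prohibition: "Missing data will not be imputed for primary analysis".
2. An option limited to the primary endpoint, identical in Protocol 10.2.3: "Imputation with mean or median may be performed where applicable for the primary endpoint as a sensitivity analysis".
3. A flat instruction: "Visit-wise mean and LOCF imputation methods will be used for missing values". Protocol 10.2.3 has no counterpart to it.

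The primary endpoint (SAP 3.1) compares rectal dose-volume between two planning scans, one before and one after injection. The repeated scores are among the secondary endpoints in SAP 3.2, for example "EPIC bowel and urinary assessment composite score at 2 weeks, 6 weeks, and 3 months post radiotherapy". The data collection table in SAP 1.6 schedules EPIC and EQ-5D-5L before RT and at 2 weeks, 6 weeks and 3 months.

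For the secondary endpoints SAP 3.2.2 plans means and SDs, and adds "Specific variables may also include additional statistics such as median, interquartile range (IQR) and confidence intervals". It also states "A parametric method of paired t-test or wilcoxon signed-rank non parametric test will be used for before and after clinical assessments". SAP 3.2.1 says "No formal tests of hypotheses are proposed for secondary endpoints", and SAP 5.2.2 says of the post-procedure data "No formal statistical testing will be performed".

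SAP 3.1.2 raises the sample size from 14 to up to 20 to allow for missing data, without giving a missing rate. SAP 7.3 uses visit completers as denominators.

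**The concern.** The third statement cannot be programmed as it stands. Visit-mean filling and LOCF put different values into the same empty cell, and the SAP does not say which applies to which endpoint, at which visit, or in which analysis. Both methods presuppose a series of visits, which a single pre/post planning comparison does not provide. EPIC and EQ-5D-5L do provide one, so a programmer looking for somewhere to apply the rule would most naturally choose them.

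Applied there, each method does its own damage. Visit-mean filling adds values with no spread around the mean and counts them as real observations, so standard errors come out too small and the paired tests reject too often. LOCF that carries a pre-RT score into a missing 2-week visit records no change for that subject and pulls the acute effect toward zero.

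Missing questionnaires are likely. For subjects irradiated before study start, the examples of retrospective data in SAP 1.1 are radiotherapy data, adverse events and MRI; questionnaires are not mentioned, though the list is only illustrative. Protocol 13 does not count missing retrospective data as deviations. SAP 4.1 nevertheless places every subject irradiated after injection in the effectiveness set. With at most 20 subjects, a few filled values are a sizeable share of the data, and SAP 2 foresees use in manuscripts and regulatory submissions.

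**Working it through.** **Inputs.** n = 20 and m = 14 are the SAP's own figures (3.1.2). The SAP states no missing rate, so m = 14, 16 and 18 observed of 20 are assumed (30%, 20%, 10% missing). The 30% case is what 14/(1 − d) = 20 implies; it is not a stated per-visit rate. Also assumed: missingness unrelated to outcome, a two-sided 5% level (none is stated for the paired tests), equal variances before and after RT, and a pre/post correlation ρ of 0.3 to 0.7. The SAP has no calculation of its own to reproduce here.

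**Step 1. Visit mean with visit-mean filling.** Filled values add nothing to the sum of squares, but the divisor becomes n − 1:

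- SD ratio = √[(m − 1)/(n − 1)]
- SE ratio = SD ratio × √(m/n)
- coverage of the nominal 95% interval = 1 − 2·P(T with m − 1 df > 2.093 × SE ratio), where 2.093 is the t quantile on 19 df

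For m = 14: SD ratio = √(13/19) = 0.827; SE ratio = 0.827 × √0.7 = 0.692; coverage = 1 − 2·P(T₁₃ > 1.448) = 0.829.

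| Observed of 20 | SD ratio | SE ratio | Coverage |
|---|---|---|---|
| 14 | 0.827 | 0.692 | 82.9% |
| 16 | 0.889 | 0.795 | 88.3% |
| 18 | 0.946 | 0.897 | 92.2% |

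**Step 2. Mean change from pre-RT, only the follow-up score filled.** With unit variances, the estimator's true variance is 1/m + 1/n − 2ρ/n. The expected reported variance is [1 + (m − 1)(1 − 2ρ)/(n − 1)]/n. At ρ = 0.5 these are 1/m and 1/n, so the reported SE is √(m/n) of the true SE: 0.84, 0.89, 0.95 for m = 14, 16, 18. For ρ from 0.3 to 0.7 the ratio stays within about 0.01 of these values.

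The SD of the change scores need not fall. At m = 14 it ranges from about 0.95 of its true value (ρ = 0.3) to 1.10 (ρ = 0.7). The SE is still too small.

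**Step 3. Error rate of the planned paired tests.** Simulation with n = 20, bivariate normal scores, no true change and ρ = 0.3, 0.5, 0.7:

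| Analysis | 14 observed | 16 observed | 18 observed |
|---|---|---|---|
| Paired t, follow-up filled with visit mean | 9–10% | 7–8% | 6% |
| Wilcoxon signed-rank, same filling | about 9% | about 7% | about 6% |
| Paired t, both scores of the pair filled | 17% | 12% | 8% |
| Paired t, LOCF from pre-RT | about 5% | about 5% | about 5% |
| Paired t, observed pairs only | about 5% | about 5% | about 5% |

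The row with both scores filled is a worst case; neither document says it will occur. LOCF does not inflate error when nothing has changed; its problem is bias when something has.

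**Step 4. LOCF and the size of the change.** If the pre-RT score is carried into a missing 2-week visit, the expected mean change is (m/n) × true change. For an assumed true fall of 10 points this gives 10 × 0.7 = 7.0, 10 × 0.8 = 8.0 and 10 × 0.9 = 9.0. Visit-mean filling gives 10.0 on average. The two permitted methods therefore differ by 3, 2 or 1 points on the same data. The gap scales with the assumed change and vanishes if there is none.

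At later visits the bias can reverse. With assumed changes of −10 at 2 weeks and −6 at 6 weeks, carrying the 2-week score forward for 30% of subjects gives 0.7 × (−6) + 0.3 × (−10) = −7.2 at 6 weeks, an overstatement. If bowel change persists for a year or more, as Protocol 4.1 cites, the bias from carrying a post-RT score to 3 months may be small.

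**The case against.** The strongest reply is that the disputed sentence follows directly on the sensitivity-analysis sentence and may only name its methods. On that reading no main EPIC or EQ-5D-5L result is imputed. Other text also leans toward observed-case reporting: SAP 3.2.2 requires the number of observations, and SAP 7.3 uses visit completers as denominators. The harm depends on conditions the SAP does not state: that the rule reaches the secondary endpoints, governs a main analysis, and feeds the tests or intervals. The study is descriptive, with no formal secondary hypotheses, so an inflated error rate has no decision attached. At 18 of 20 observed the error rate is about 6%, close to nominal. Protocol 10.3 lets the SAP add methods, so the sentence's absence from the protocol is not itself a fault.

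Much of this stands. The sensitivity-only reading is possible, the harm is conditional, and no confirmatory claim is threatened. But the sentence does not say it is a sensitivity analysis, and its change from an optional to a mandatory verb points the other way. LOCF and visit-wise filling also fit the primary endpoint poorly. The observed-case wording elsewhere does not cancel an explicit instruction to impute. SDs and intervals are themselves descriptive outputs, and SAP 3.2.2 says the paired tests will be run, so their p-values will be produced. The validation in SAP 6 might expose a disagreement between programmers, but could not say which method was intended.

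**Conclusion.** The concern holds. SAP 4.3 ends with a mandatory imputation rule that has no scope and names two methods giving different answers. If it is applied to EPIC and EQ-5D-5L, visit-mean filling understates the SE of a visit mean by about 31%, 21% or 10% with 14, 16 or 18 of 20 observed, and roughly doubles the paired-test error rate in the first case. LOCF from pre-RT removes 30%, 20% or 10% of any change at 2 weeks.

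These sizes rest on the assumed missing shares, missingness unrelated to outcome, a 5% level and, for the point differences, an assumed 10-point fall. The defect in the text depends on none of them. What is affected is the reported SDs, any confidence intervals and the paired p-values for secondary endpoints. It should be fixed before analysis, but it does not undermine the study.

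**What to change.** Delete the last imputation sentence of SAP 4.3. Alternatively, confine it to a named and labelled sensitivity analysis of EPIC and EQ-5D-5L that says which method applies when, and keep the filled values out of the paired tests and confidence intervals.

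In either case, state that:

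- EPIC and EQ-5D-5L are summarised on observed cases, with n at each visit;
- paired tests use only subjects with both scores observed;
- the yes/no MRI endpoints at 6 weeks and 10 months are not imputed, in line with the completer denominators in SAP 7.3.

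The cost is a short SAP rewording and little reprogramming, with no new data. Because the sentence is not in Protocol 10.2.3, no protocol change is needed. Intervals will be wider than with filled values. For a visit mean, the filled interval is 0.67, 0.78 or 0.89 times as wide as the observed-case interval at 14, 16 or 18 observed (SE ratio × t quantile on 19 df ÷ t quantile on m − 1 df). The wider interval reflects the information actually collected.
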